**1. Main hypothesis:**

- Patients admitted for COVID-19 present a progressive loss of mass muscle, both due to the inflammatory state, decreased intake, bedridden due to hospitalization and derivative of treatment (eg corticosteroid therapy).

**2. Main objective:**

- Quantify the loss of muscle mass in hospitalized patients in areas of Medicine Inmate diagnosed with COVID-19.

**3. Secondary objectives:**

- Analyze the clinical characteristics and prevalence of sarcopenia in patients included in the study.
- Analyze the thickness and cross-sectional area of the muscles in all patients rectus femoris, vastus medialis, vastus lateralis, medial calf and the angle of pennation of the medial twin.

- Analyze the correlation between ultrasound parameters and analytical parameters (nutritional, inflammatory).
- Determine the relationship between muscle loss and treatment received (dexamethasone, methylprednisolone, prednisone).

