### ***11. Study population and total number of patients***

Patients over 18 years of age who are admitted to the hospital and whose primary diagnosis and reason for staying is COVID-19 pneumonia. The prevalence of sarcopenia in hospitalized patients is 15-20%. Assuming a alpha risk of 0.05 and beta risk of 0.2 in a one-sided contrast, 64 subjects are required to detect a difference equal to or greater than 20% loss of muscle mass. It has been an estimated loss to follow-up rate of 0%.

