**Presentation to CEIC: February 2021.**

**Data collection: March 2021.**

**Analysis of results: April 2021**

**Preparation of articles, communications: April 2021.**

*F. Reason for the project.*

The COVID-19 pandemic is having a devastating global impact, and adults Older people who suffer from it have a higher risk of death from the disease. Nevertheless, survivors of the disease are at greater risk of suffering from diseases such as sarcopenia, more common in younger adults and with greater severity of disease.

Sarcopenia (from the Greek terms “*sarx*” (meat) and “*penia*” (poor quality)) today it is considered one of the most relevant syndromes, and the substrate of many of the health problems of the elderly and hospitalized patients, increasing by itself morbidity and mortality, and of course reducing activity and functional recovery. Of fact is deeply related to frailty, functional decline, falls, osteoporosis and different metabolic disorders (hydrocarbon intolerance) and homeostasis (thermoregulation) of the elderly. Sarcopenia is present in the 5-13% of people between 60 and 70 years old and in 11- 50% of the population over 80 years.

The diagnosis of sarcopenia has advanced in recent years by establishing itself in different consensus homogeneous criteria that necessarily combine two elements: general loss of strength accompanied by loss of muscle mass skeletal. Today there are three consensus for the diagnosis of sarcopenia: the international (IWGS), European (EWGSOP), and the most recent of a cohort American (FNIH). In all of them, the measurement of skeletal muscle mass constitutes one of the two diagnostic criteria.

The main methods to measure this muscle loss that are established are the imaging techniques (computerized tomography (CT), magnetic resonance imaging (MRI), Dual energy X-ray absorptiometry (DEXA) and ultrasound.

The most common ultrasound measurements used for this purpose are thickness muscle (cm) at the point of the ultrasound path of maximum muscle thickness, the area of

cross section (area calculated by the basic software at the point of maximum muscle thickness), and the angle of pennation (angle formed between the muscular fascia deep and muscle fibers). The first two measurements can be made in several long muscles, while the pennation angle is usually performed mainly in the medial gastrocnemius muscle (internal twin). They are easy to obtain, bloodless and reproducible.

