#### *c. Inclusion and exclusion criteria.*

Patients who meet the following criteria will be included:

- Over 18 years old, men or women.
- Main diagnosis is pneumonia due to COVID-19

- Subjects who, after having received the information on the design, the purposes of the project, the possible risks that may arise from it and that in any moment they can deny their collaboration, verbally grant their consent to participate in the study.

The exclusion criteria to participate in the study are:

- Refusal of the patient to participate in the study.
- Present a malignant neoplasm in active phase except Ca spino- or basal cell in local stage
- Clinical situation of agony.
- Amputation of limb (s).

*d. Origin of the data:*

The data will be collected prospectively.

*and. Schedule and expected date of completion:*

The study will begin in **February 2021**, with an estimated duration of **3 months** (1 month for application, 1 month for data collection, 1 month for results analysis and preparation of articles and / or communications).

*and. Sample size:*

Patients over 18 years of age who are admitted to the hospital and whose primary diagnosis and reason for staying is COVID-19 pneumonia. For a 95% confidence interval, with a precision level of 3%, an estimated loss in about 3% of muscle mass in COVID-19 patients for an admission less than 10 days, we hope to recruit 124 patients. A loss to follow-up rate has been estimated 0%.

Subjects will be followed up during hospitalization and one month after consultation. recruitment. The 30-day follow-up will be done by reviewing the history

clinic, and a telephone contact will be made.

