***and. Nutritional Variables:***

o **Current weight and height** : if it cannot be measured, self-reported.

o **Recent weight loss**

o Measurement of **muscle strength** , using **dynamometry** (average of 3 measurements)

in dominant arm.

o **Circumference of the calf.**

o Body composition using **impedance** measurement (BIA) that estimates the **mass muscular skeletal muscle.**

o Pass the **SARC-F questionnaires** , as a universal screening method: 5 questions in less than 1 minute.

o Establish criteria for malnutrition ( **MUST questionnaire** ) and **frailty** (criteria Friend).

*Minnesota Brief Physical Activity Questionnaire*

*F. Treatment-related variables:*

- Treatment according to clinical practice: drug, duration and dose.

*g. Variables related to evolution:*

- Degree of functional recovery at 30 days (Barthel scale) and quality questionnaire life (EuroQol-5D). Adverse events or complications during the next 30 days of admission. Any event will be considered **complications after 30 days** unexpected event requiring treatment or medical attention, within 30 days of the episode (whether hospitalized or not), generally clinical worsening, readmission or mortality.

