**Table 1. Study development**

*and. Statistic analysis*

The variables will be expressed by total numbers and percentages for the variables categorical, and central values with measures of dispersion (mean and standard deviation / median and interquartile range if not normal distribution) for quantitative variables.

For the comparisons, the following statistical tests will be carried out: Chi and obtaining of the odds ratio with 95% confidence intervals (for the comparison of variables qualitative); Student's t (and Spearman test) (to obtain the difference of means / ranges); and Pearson's R (to determine the correlation between the variables quantitative). The data will be analyzed using SPSS statistical analysis software.

20.0.

Data in absentia will not be charged and will be left as lost.

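### Sarcopenia prevalence: a patient too weak for dynamometry gets no sarcopenia status under the missing-data rule, so the reported figure is likely to be too low

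*Combined protocol and SAP*

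**What the plan says.** - **Objective.** The first secondary objective, in the Summary and again in Section 2.g, is to "Analyze the clinical characteristics and prevalence of sarcopenia in patients included in the study". The target is everyone enrolled.
- **Criteria.** The rationale (Summary item 9 and Section 2, Reason for the project) says the consensus criteria "necessarily combine two elements: general loss of strength accompanied by loss of muscle mass skeletal". It names three consensuses. It does not choose one or give cut-offs.
- **Strength measure.** Section 4, Nutritional Variables, lists dynamometry in the dominant arm, recorded as an "average of 3 measurements". No other direct strength measurement is listed; SARC-F appears only as a screening questionnaire. In the same list, weight and height have a fallback ("if it cannot be measured, self-reported"). Dynamometry has none.
- **Missing data.** Section 5, Statistic analysis, has one rule for all variables: "Data in absentia will not be charged and will be left as lost". Allowing for the translation, I read this as no imputation. No exception and no sensitivity analysis is described.
- **Who can enter.** The only exclusion based on how ill the patient is reads "Clinical situation of agony" (Section 3.c). Inclusion also requires the patient's verbal consent, and the main objective concerns internal-medicine areas.

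**The concern.** Inability to perform a strength test is itself information about strength. A patient who is too weak to grip has in effect shown low strength, yet under the stated rule has no strength value and cannot be classified. The patients lost in this way are not a random subset. Unless low muscle mass is unusually rare among them, sarcopenia is more common in this group than among those tested.

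The reported prevalence would then describe patients fit enough to be tested, whereas the objective speaks of the patients included. A larger sample would not remove the error. If the reason for a missing reading is not recorded at the bedside, an analyst cannot later separate patients who were too weak from those in whom the test was never attempted.

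**Working it through.** **The plan's own figure.** Section 3 states "For a 95% confidence interval, with a precision level of 3%, an estimated loss in about 3% of muscle mass in COVID-19 patients" and arrives at 124 patients. The single-proportion precision formula gives 1.96² × 0.03 × 0.97 / 0.03² = 124.2, so 124 reproduces (125 if rounded up). It does not depend on dynamometry; I use it below only for the sampling error.

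**Inputs.**
- *p*, prevalence among tested patients: 15% or 20%, from Summary item 11 ("The prevalence of sarcopenia in hospitalized patients is 15-20" per cent).
- *u*, share untested: not in the documents. Assumed 5–20%.
- *q*, share of the untested who are sarcopenic: not in the documents. Assumed 40–60%. For patients too weak to grip, *q* is the share with low muscle mass.

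**Formulas.**
- All-patient prevalence = *p*(1 − *u*) + *qu*.
- Untested dropped: reported figure *p*; shortfall *u*(*q* − *p*).
- Untested counted as non-cases: reported figure *p*(1 − *u*); shortfall *qu*.

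**All-patient prevalence (*q* = 40% to 60%).**

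| *u* | *p* = 15% | *p* = 20% |
|---|---|---|
| 5% | 16.25% to 17.25% | 21.0% to 22.0% |
| 10% | 17.5% to 19.5% | 22.0% to 24.0% |
| 20% | 20.0% to 24.0% | 24.0% to 28.0% |

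For example, 0.15 × 0.80 + 0.60 × 0.20 = 0.24. If the untested are dropped, a reported 15% is low by 1.25 to 9 points and a reported 20% by 1 to 8 points. If they are kept as non-cases, the shortfall *qu* runs from 0.05 × 0.40 = 2 points to 0.20 × 0.60 = 12 points.

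**Direction.** With the untested dropped, the figure is too low when *q* > *p*, correct when *q* = *p*, and too high when *q* < *p*. At *u* = 10% and *q* = 10% it is too high by 0.5 point (*p* = 15%) or 1.0 point (*p* = 20%). With the untested counted as non-cases, it is too low whenever any of them is sarcopenic.

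**Against sampling error.** The 95% half-width with 124 patients is 1.96 × √(0.15 × 0.85 / 124) = 6.3 points at 15%, and 7.0 points at 20%. With the untested dropped and *p* = 15%, the shortfall passes 6.3 points at *u* = 20% only if *q* exceeds 0.15 + 0.063/0.20, about 46%. At *u* = 10%, *q* would have to reach about 78%, outside the assumed range.

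**Bounds with no assumption about *q*.** The limits are *p*(1 − *u*) and *p*(1 − *u*) + *u*. At *u* = 10%, a complete-case 15% is compatible with 13.5% to 23.5%, and 20% with 18% to 28%. The lower limit lies below the complete-case figure, so that figure is not itself a bound.

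**The case against.** The strongest reply is that the documents do not show many patients would be untestable, or what would be done with them. Much of this stands.

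- **Number affected.** A reader might infer from the Annex I fields for ventilation, amines and ECMO that such patients are enrolled and cannot grip. The documents do not support that. Patients must be informed and give verbal consent, no proxy route is described, and the setting is internal medicine. Those fields can record escalation later in the stay.
- **The form.** A reader might infer that the data collection form has no place to record inability. This cannot be asserted: Annex I has a separate dynamometry heading whose content is not available in the text reviewed. What can be said is that Sections 4 and 5 give no rule for such patients.
- **Handling.** No case definition or denominator is stated, so it is inference that untested patients leave the denominator. This does not rescue the figure, because keeping them as non-cases lowers it further. The timing of the test and the use of fewer than three readings are also unspecified, so a later or partial reading is not ruled out.
- **Direction.** Readings may be missing for reasons unrelated to weakness; Section 4 itself cites limited time and healthcare pressure. For patients who miss the test through acute illness, the direction is less certain.

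What remains is that patients too weak for the test have no route to a sarcopenia status, although the objective covers everyone included.

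**Conclusion.** The point holds as a likely understatement in a secondary objective. The stated rule leaves patients too weak for dynamometry unclassified, and the prevalence will then be too low if low muscle mass among them is more common than sarcopenia among those tested. That is a weak condition, but it is an assumption. It would be too strong to say that the plan demonstrably biases prevalence low or that the bias is large.

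The size rests wholly on assumed inputs. With 5–20% untested and 40–60% of them sarcopenic, a complete-case 15% stands for about 16–24%, and 20% for 21–28%. Verbal consent and the setting make the low end more plausible. The primary ultrasound measure and the sample size are unaffected. The absence of an operational definition of sarcopenia is a wider gap behind the same objective; it needs its own correction and does not remove this one.

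**What to change.** 1. **Data collection form.** Beside dynamometry, record why it was not done: *too weak*, *acute illness or other clinical reason*, or *not attempted*.
2. **Section 5, Statistic analysis.** Make one exception to the missing-data rule: for the prevalence of sarcopenia, *too weak* counts as meeting the strength criterion. The muscle-mass criterion must still be met, by whatever measure and cut-off the plan adopts.
3. **Reporting.** Give this prevalence beside the complete-case figure and the number untested by reason.
4. **Sensitivity analysis.** Repeat with *acute illness or other clinical reason* also counted as low strength. This does not belong in the main figure, because acute illness does not by itself establish low strength.
5. **Bounds.** Show the prevalence over all included patients with every unclassified patient as a non-case, then as a case. This also covers patients whose muscle-mass value is missing.

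The cost is one coded field, a few sentences in the analysis section and a few table rows. The drawback is that some acute weakness may be counted as low strength; the side-by-side figures show how much this matters.

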#### **9. Rationale**

The COVID-19 pandemic is having a devastating global impact, and adults Older people who suffer from it have a higher risk of death from the disease. Nevertheless, survivors of the disease are at greater risk of suffering from diseases such as sarcopenia, more common in younger adults and with greater severity of disease.

Sarcopenia (from the Greek terms “*sarx*” (meat) and “*penia*” (poor quality)) today it is considered one of the most relevant syndromes, and the substrate of many of the health problems of the elderly and hospitalized patients, increasing by itself morbidity and mortality, and of course reducing activity and functional recovery. Of fact is deeply related to frailty, functional decline, falls, osteoporosis and different metabolic disorders (hydrocarbon intolerance) and homeostasis (thermoregulation) of the elderly. Sarcopenia is present in the 5-13% of people between 60 and 70 years old and in 11- 50% of the population over 80 years.

The diagnosis of sarcopenia has advanced in recent years by establishing itself in different consensuses homogeneous criteria that necessarily combine two elements: general loss of strength accompanied by loss of muscle mass skeletal. Today there are three consensuses for the diagnosis of sarcopenia: the international (IWGS), European (EWGSOP), and the most recent of a cohort American (FNIH). In all of them, the measurement of skeletal muscle mass constitutes one of the two diagnostic criteria.

The main methods to measure this muscle loss that are established are the imaging techniques (computerized tomography (CT), magnetic resonance imaging (MRI),

Dual energy X-ray absorptiometry (DEXA) and ultrasound.

The most common ultrasound measurements used for this purpose are thickness muscle (cm) at the point of the ultrasound path of maximum muscle thickness, the area of cross section (area calculated by the basic software at the point of maximum muscle thickness), and the angle of pennation (angle formed between the muscular fascia deep and muscle fibers). The first two measurements can be made in several long muscles, while the pennation angle is usually performed mainly in the

medial gastrocnemius muscle (internal twin). They are easy to obtain, bloodless and reproducible.

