#### **Four. V ARIABLES IN EVALUATION**

Data to collect:

\* PRIMARY VARIABLE:

*to. Variables related to ultrasound:*

To collect these variables, the GE VENUE will be used, the linear probe will be used (5.5–7.5 MHz) (General Electrics Healthcare, Madrid, Spain).

All patients will undergo a muscle ultrasound upon admission to the center and prior to upon discharge, using the usual muscle sweep technique. The ultrasound will be performed on the rectus femoris, vastus medialis, vastus lateralis and medial calf muscles. They will be measured:

- Muscle thickness in its cross section (in mm), in the plane of maximum thickness

in longitudinal sweep

- Cross-sectional area (in  $\text{cm}^2$ ) in the plane of maximum area in the scan longitudinal
- Angle of penetration (in degrees) of the medial twin, using the base of the angle the deep muscle fascia and as an angle the maximum inclination of the you muscle mass.

This exam will be carried out by 5 experienced physicians according to the criteria of the ACEP (American College of Emergency Physicians) and who carry out more than 10 studies ultrasounds per week and at least 3 years of experience in the performance and interpretation of ultrasound examinations. A reliability study will not be conducted given the limitation in the time and current healthcare pressure.

In addition, to avoid the possible bias that inter-operator variability would suppose in these circumstances, the research team was provided with a training program and designed internal training consisting of:

- Theoretical course on basic, systematic musculoskeletal ultrasound, medication, etc.
- Practical seminars in which an ultrasound machine and healthy models will be used to your measurement.
- Supervised practical training with real hospital patients until assessing an adequate measurement of at least 5 patients.
- The team of 5 doctors adequately trained in this technique were specific to this trial to avoid protocol deviations and any other form of interoperator variability.

\* SECONDARY VARIABLES:

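### If muscle levels are correlated, the unadjusted ultrasound-laboratory correlations in a pooled adult cohort can partly reflect age, sex or body size; the plan should state level or change and add adjusted coefficients

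*Combined protocol and SAP*

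**What the plan says.** The objective appears in the Summary (item 10, Secondary objectives) and again in section 2.g: "Analyze the correlation between ultrasound parameters and analytical parameters (nutritional, inflammatory").

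The method comes from the Statistic analysis part of section 5. It introduces its list with "For the comparisons, the following statistical tests will be carried out" and names chi-square with odds ratios, Student's t with a Spearman test for differences, and "Pearson's R (to determine the correlation between the variables quantitative"). No regression, partial correlation, stratification or covariate is named there or elsewhere.

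The cohort (section 3.c) is "Over 18 years old, men or women", with no upper age limit.

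The primary ultrasound variables (section 4) include "Muscle thickness in its cross section (in mm), in the plane of maximum thickness" and a cross-sectional area in cm2 taken "in the plane of maximum area in the scan longitudinal". Neither is indexed to height or weight. The pennation angle of the medial calf muscle, in degrees, is also recorded. On timing, "All patients will undergo a muscle ultrasound upon admission to the center and prior to upon discharge".

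Age and sex are listed among the demographic variables, and weight and height among the nutritional variables and on the CRF. No analysis uses them.

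**The concern.** Thickness in mm and area in cm2 can be expected to differ between men and women, between taller and shorter patients, and between younger and older ones. Some of the listed laboratory values may differ along the same lines. If both do, pooling everyone creates a correlation between them even when, among patients of the same age, sex and height, the marker tells nothing about muscle.

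This matters because of how the result would be read. The main hypothesis names inflammation and reduced intake among the causes of muscle loss. A crude coefficient with albumin, prealbumin, CRP or IL-6 invites a reading as support for that hypothesis, and an unadjusted pooled coefficient cannot separate it from differences in who the patients are.

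**Working it through.** **Inputs from the documents.** The Sample size part of section 3 gives n=124; Summary item 11 gives n=64. No figure is attached to the correlation objective itself. The 124 reproduces as a precision calculation: 1.96² × 0.03 × 0.97 / 0.03² = 124.2. The two sample sizes need reconciling separately; both are carried here because the point does not depend on which is right.

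**Assumed inputs.** The documents give no correlation of muscle size or of any marker with age, sex or height. The values below are assumptions shown as a range. The true link after adjustment is set to zero throughout, and tests are two-sided at 0.05.

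**Induced correlation.**
- Age alone: r = (correlation of muscle with age) × (correlation of marker with age).
- Sex alone, 50:50 split, difference of d SD on both variables: r = 0.25d² / (1 + 0.25d²). At d=1 this is 0.25 / 1.25 = 0.20.

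**Chance of p<0.05.** With Fisher's z, let λ = atanh(r) × √(n−3). The probability is Φ(λ−1.96) + Φ(−λ−1.96). For r=0.16 and n=124, λ = 0.1614 × 11 = 1.775 and Φ(−0.185) = 0.427.

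| Assumption (both variables) | Induced r | p<0.05, n=124 | p<0.05, n=64 |
|---|---|---|---|
| Unrelated to age or sex | 0 | 5% | 5% |
| Age correlation 0.2 | 0.04 | 7% | 6% |
| Age correlation 0.3 | 0.09 | 17% | 11% |
| Age correlation 0.4 | 0.16 | 43% | 24% |
| Age correlation 0.5 | 0.25 | 80% | 51% |
| Sexes differ by 1 SD | 0.20 | 61% | 35% |

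For the first row it is enough that one of the two variables, for example the marker, is unrelated to age and sex.

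**Age and sex together.** A simulation (4,000 runs per case, age and sex independent) compared the crude coefficient with the partial coefficient adjusted for both. The induced r is the sum of the products.

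| Case | Muscle: sex, age | Marker: sex, age | Induced r | Crude p<0.05, n=124 | n=64 |
|---|---|---|---|---|---|
| Weak | 0.2, −0.2 | 0.1, −0.2 | 0.02 + 0.04 = 0.06 | 11% | 8% |
| Moderate | 0.4, −0.4 | 0.3, −0.3 | 0.12 + 0.12 = 0.24 | 77% | 50% |
| Strong | 0.5, −0.4 | 0.4, −0.3 | 0.20 + 0.12 = 0.32 | 96% | 75% |

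After adjustment, the rate was between 4.5% and 5.6% in every case and at both sample sizes.

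**Price of adjusting.** The 95% half-width at r=0 is tanh(1.96 / √(n−k−3)) with k covariates. At n=124 it is 0.176 for k=0 (√121) and 0.178 for k=3 (√118). Even with four covariates, power to detect r=0.25 falls only from 80.2% to 78.9%.

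**The case against.** The strongest objection is that the mechanism needs levels, and the plan does not say levels. Each muscle is scanned at admission and again before discharge, and the main objective and the treatment objective both concern loss. If percent change within patients is what gets correlated, much of the fixed sex and size difference cancels, although age may still matter. This stands, and it makes the point conditional. The correlation objective does speak of parameters where the neighbouring objectives speak of muscle loss, which suggests levels, but that is a hint and not a commitment.

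Second, a reader might infer that the protocol itself shows muscle size to depend strongly on age, because its Rationale reports sarcopenia in "5-13% of people between 60 and 70 years old and in 11- 50% of the population over 80 years". The documents do not support that much. These are prevalences of a diagnosis that combines strength and mass, the two ranges overlap, and they cover only people from 60 upwards. The same Rationale describes sarcopenia among COVID-19 survivors as commoner in younger adults. That muscle size depends on sex and height, and that particular markers vary with age or sex, is plausible but has no source in the documents. The case is also less developed for CRP and IL-6 than for the nutritional markers, and the pennation angle is not a size measure.

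Third, the objective is descriptive. It asks for a correlation and makes no claim of independent association, so a crude coefficient does answer it as written. This also stands. What remains is the interpretation that the nutritional and inflammatory labels invite.

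Finally, some of the effect of age may act through nutrition, so adjustment can remove part of a real pathway. That is a reason to show both coefficients, not to omit the adjusted one.

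**Conclusion.** The point holds as a conditional and minor one. The plan pools men and women of all adult ages, uses unindexed thickness and area, names only bivariate correlation, and leaves unused the covariates it collects. If levels are correlated, the crude coefficient can reflect age, sex or body size. How far is unknown: the chance of a nominally significant result without any true adjusted link runs from about 5% for a marker unrelated to these factors, through 7% to 17% for weak dependence on age, to 43% to 80% for moderate to strong dependence at n=124, and is lower at n=64.

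A reader might go further and infer that the planned correlations will be confounded, or that the study's findings on muscle loss are compromised. The documents support neither. They give no strength of dependence, they leave level or change open, and the main objective of quantifying loss does not use these coefficients.

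**What to change.** In the Statistic analysis part of section 5, add one or two sentences for this objective:

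- State whether the ultrasound value correlated is the admission level, the discharge level or the within-patient percent change.
- Report partial correlations (on ranks where distributions are skewed), or a linear model of the ultrasound measure on the marker, adjusted for age, sex and height, beside the crude coefficient.
- State that any nutritional or inflammatory interpretation rests on the adjusted value.

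No new data are needed, since age, sex and height are already collected; height may be self-reported where it cannot be measured. The cost is three degrees of freedom and a 95% half-width at r=0 of about 0.178 instead of 0.176 at n=124. Because missing values will not be imputed, a patient lacking height would drop out of the adjusted analysis, so the number of patients behind each coefficient should be shown.
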